6.2.2. MMRM

Analysis of continuous efficacy and health outcome variables collected at multiple postbaseline visits during a study period will be made using MMRM analysis using a model that includes treatment, geographic region (US/OUS), previous therapy (yes/no), baseline value, visit, and the interaction of treatment-by-visit as fixed factors. MMRM details are provided in Section 6.1.3.

6.2.3. ANCOVA

Analysis of continuous efficacy and health outcome variables collected at one postbaseline visit during a study period and for sensitivity analyses will be made using ANCOVA using a model that includes baseline value as a continuous covariate and treatment, geographic region (US/OUS), and previous therapy (yes/no) as fixed factors. ANCOVA details are provided in Section 6.1.3.

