The analysis method for comparisons of each Induction Period LY3074828 dose regimen (300 mg, 100 mg, 30 mg) and placebo for the continuous efficacy and health outcome variables will be a Mixed effect Model Repeat Measurement (MMRM) analysis when the endpoint is collected at multiple postbaseline visits during a study period, or analysis of covariance (ANCOVA) when the endpoint is collected at one postbaseline visit during a study period, or for sensitivity analyses. When the MMRM model is used, the model will include treatment, geographic region (US/OUS), previous therapy (yes/no), baseline value, visit, and the interaction of treatment-by-visit as fixed factors. When the ANCOVA model is used, the model will include baseline value as a continuous covariate and treatment, geographic region (US/OUS), and previous therapy (yes/no) as fixed factors. For both models, the covariance structure to model the within-patient errors will be unstructured. The Restricted Maximum Likelihood (REML) will be used. The Kenward-Roger method will be used to estimate the denominator degrees of freedom. If the unstructured covariance matrix results in a lack of convergence, the heterogeneous Toeplitz covariance structure, followed by the heterogeneous autoregressive covariance structure, followed by the compound symmetry will be used. This order is specified according to a decreasing number of covariance parameters in the structure. Type III tests for the least squares (LS) means will be used for the statistical comparison; the 95% CI will be reported. Dosing regimen comparisons at Week 16 (Visit 7) and all other postbaseline visits in the Induction Period will be reported.

Proportions and 95% confidence intervals will be summarized for binary outcomes observed in the Maintenance Period. Mean change from baseline and 95% confidence intervals will be summarized for continuous outcomes observed in the Maintenance Period.

The Kaplan-Meier product limit method will be used to estimate the survival curves for post induction (includes Maintenance and Follow-up Periods) time-to-event variables (time to loss of response, time to response recapture after loss of response); median times will be summarized by treatment.

Time to First Loss of Response in the Maintenance Period for PRN Patients

Time to first loss of response (PASI 90 or PASI 100) in the Maintenance Period includes only those subjects who achieved the respective response at Week 16 and is defined in weeks as:

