6.3.2. MMRM

MMRM will be the primary analysis method for longitudinal continuous measurements. It assumes missing data can bias results but the bias can be attenuated by modeling random effects using the within-subject error correlation structure. These correlations between the repeated measurements provide the platform used to account for the bias from subject dropout. MMRM model details are provided in Section 6.1.3.

If subjects enter the Rescue Period, only the visits prior to entering the Rescue Period will be included in the MMRM model for the Maintenance Period efficacy analysis.

6.3.3. mBOCF

An mBOCF analysis will be performed on key continuous efficacy endpoints in the Induction Period only, including PASI, BSA, PSSI, and PSS.

The above is proposed as a sensitivity analysis. For patients discontinuing investigational product due to an AE, the baseline observation will be carried forward to the corresponding primary endpoint for evaluation. For patients discontinuing investigational product for any other reason, the last nonmissing postbaseline observation before discontinuation will be carried forward to the corresponding primary endpoint for evaluation. Randomized patients without at least 1 postbaseline observation will not be included for evaluation with the exception of patients discontinuing study treatment due to an AE.

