	DLQI total score and domain scores change from baseline	MMRM;	ITT Population	All pairwise comparisons against placebo at all postbaseline visits in Induction Period
		ANCOVA	Maintenance Period Efficacy Population	All visits in Maintenance Period
SF-36	SF-36 change from baseline for Domain Scores and Component Scores	ANCOVA	ITT Population	All pairwise comparisons against placebo at all postbaseline visits in Induction Period
		ANCOVA	Maintenance Period Efficacy Population	All visits in Maintenance Period
	SF-36 Physical Component (PCS) and Mental Component (MCS) Response	Logistic regression analysis with NRI	ITT Population	All pairwise comparisons against placebo at all postbaseline visits in Induction Period
		Summary statistics with NRI	Maintenance Period Efficacy Population	All visits in Maintenance Period
PatGA	Change from baseline	MMRM	ITT Population	All pairwise comparisons against placebo at all postbaseline visits in Induction Period
		ANCOVA	Maintenance Period Efficacy Population	All visits in Maintenance Period
PSS	PSS total score and item scores change from baseline	MMRM; mBOCF ANCOVA	ITT Population	All pairwise comparisons against placebo at all postbaseline visits in Induction Period
		ANCOVA	Maintenance Period Efficacy Population	All visits in Maintenance Period

Measure	Variable	Analysis Method (Sections 6.1.3)	Population (Section 6.1.1)	Time Point
		Summary statistics (As observed) or individual trajectory line plot if total number of subjects is too small	Rescue Period Efficacy Population	All visits in Rescue Period

Abbreviations: ANCOVA = analysis of covariance; BSA = body surface area; DLQI = Global Assessment Dermatology Life Quality Index; ITT = intent-to-treat; KM = Kaplan-Meier; mBOCF = modified baseline observation carried forward; MCS = Mental Component Score; MMRM = mixed model repeating measures; NRI = non-responder imputation; PASI = Psoriasis Area and Severity Index; PatGA = Patients Global Assessment of Psoriasis; PCS = Physical Component Score; PSS = Psoriasis Symptoms Scale; PSSI = Psoriasis Scalp Severity Index; sPGA = Static Physician Global Assessment.

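### SAP Table 6.3 gives ANCOVA as the only method for maintenance change in DLQI, SF-36, PatGA and PSS, although the SAP's own rule assigns MMRM to endpoints measured at several visits

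*SAP*

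**What the plan says.** **The rule.** SAP 6.2.2: "Analysis of continuous efficacy and health outcome variables collected at multiple postbaseline visits during a study period will be made using MMRM analysis". The sentence has no exception and is not limited to the Induction Period. SAP 6.2.3 gives the complement: ANCOVA is for variables "collected at one postbaseline visit during a study period" and for sensitivity analyses. SAP 6.3.2 adds that "MMRM will be the primary analysis method for longitudinal continuous measurements".

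**The table.** For the Maintenance Period Efficacy Population, the Table 6.3 row for "DLQI total score and domain scores change from baseline" lists ANCOVA, at all maintenance visits. The row for "SF-36 change from baseline for Domain Scores and Component Scores" does the same, and so do the PatGA and PSS rows. No MMRM stands beside any of them. PASI, BSA and PSSI change scores get MMRM in the same period.

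**A further description.** SAP 6.1.3: "Mean change from baseline and 95% confidence intervals will be summarized for continuous outcomes observed in the Maintenance Period". Protocol 10.3.3.2 likewise plans a by-treatment summary of change and 95% confidence interval for DLQI, SF-36 and PatGA at Weeks 52, 104 and 120.

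**Missing data and rescue.** SAP 6.3.3 limits mBOCF to Induction. SAP 6.1.2.1 ends the Maintenance Period at rescue. SAP 6.3.2 says that an MMRM keeps a rescued subject's visits up to rescue and no later ones. There is no matching sentence for ANCOVA.

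**The concern.** Mean change in these four instruments at Weeks 52 and 104 is a named secondary endpoint, yet the plan describes its analysis in ways that do not agree. An analyst following 6.2.2 fits one model to three visits, one following Table 6.3 fits a separate model at each visit, and one following 6.1.3 reports raw means.

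These can give different numbers. Rescue is triggered by poor PASI response, and subjects who are doing badly may also be more likely to leave. A by-visit analysis of those who remain then describes a selected, better group. The binary and continuous results for the same instrument also part company. For DLQI and SF-36 responses, SAP 6.3.1 counts visits after rescue as non-response, while the change scores simply lose those subjects.

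**Working it through.** **1. Does the one-visit condition for ANCOVA hold?**

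| Instrument | Postbaseline visits in Induction | Table 6.3, Induction | Scheduled visits in Maintenance | Table 6.3, Maintenance |
|---|---|---|---|---|
| SF-36 | 1 (Week 16) | ANCOVA | 3 (Weeks 32, 52, 104) | ANCOVA |
| DLQI | several | MMRM | 3, plus PRN-dosing and rescue visits | ANCOVA |
| PatGA | several | MMRM | 3 | ANCOVA |
| PSS | several (daily diary) | MMRM, with mBOCF ANCOVA | 3 | ANCOVA |

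The visits come from the Protocol Schedule of Activities, the Week 104 endpoint in the Protocol Synopsis and the PSS windows in SAP Appendix 2. In Induction the table follows the rule: the one-visit instrument gets ANCOVA and the others MMRM. In Maintenance all four have three visits, so the MMRM condition is met and the ANCOVA condition is not. The sensitivity-analysis clause does not cover these rows, because no primary MMRM is listed for them.

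The 6.1.3 wording that MMRM is the "analysis when the endpoint is collected at multiple postbaseline visits during a study period" sits in a sentence about Induction comparisons with placebo. The conflict therefore rests on 6.2.2, 6.2.3 and 6.3.2, which carry no such limit.

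**2. Who drops out of a by-visit ANCOVA?**

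The ANCOVA in 6.2.3 contains baseline, treatment, region and previous therapy, with no visit term. A subject needs an in-period value at the visit analysed.

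| Subject | By-visit ANCOVA, Weeks 52 and 104 | MMRM over Weeks 32, 52, 104 |
|---|---|---|
| PRN, rescued between Weeks 32 and 52 | contributes nothing | Week 32 score used |
| Leaves the study between Weeks 32 and 52 | contributes nothing | Week 32 score used |
| Rescued or left before Week 32 | contributes nothing | no scheduled in-period score to use |
| Stops treatment only | visits continue (Protocol 8.1.1) | visits continue |

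Rescue applies to PRN subjects only (SAP Table 5.1). In the 300 mg Q8W group, values are lost only through study withdrawal or missed visits.

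**3. Size, on assumed inputs.**

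The plan states no figure for this analysis. Its one design figure, power over 99% for 60% versus 3% with 50 per arm, reproduces (exact Fisher power 0.9999999) but has no bearing here.

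Assumptions, because the documents give none: Week 32 and Week 52 change scores in SD units with correlation ρ from 0.4 to 0.8; a fraction d from 10% to 30% lost between the two visits; and 60% × 50 = 30 subjects per PRN arm. Lower scores are better.

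*Loss more likely with a worse Week 32 score* (logistic, slope 1.5 per SD, 4,000 simulated trials per setting). Bias of the Week 52 mean in SD, negative meaning too favourable:

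| ρ | 10% lost | 20% lost | 30% lost |
|---|---|---|---|
| 0.4 | −0.049 | −0.087 | −0.131 |
| 0.6 | −0.070 | −0.144 | −0.205 |
| 0.8 | −0.092 | −0.186 | −0.266 |

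The likelihood-type estimate that also uses Week 32 is within 0.01 SD of the truth in all nine settings.

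*Extreme case: exactly the worst fraction d at Week 32 is lost.* Bias = −ρ·φ(z)/(1 − d), with z the 1 − d normal quantile.
- ρ = 0.4, d = 0.1: −0.4 × 0.1755 / 0.9 = −0.078.
- ρ = 0.8, d = 0.3: −0.8 × 0.3477 / 0.7 = −0.397.

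*Loss driven by a PASI-like variable instead* (assumed PASI–PRO correlation 0.4 to 0.7). The observed-only bias was 0.09 to 0.26 SD. Using the Week 32 PRO score removed 23% to 79% of it, not all.

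**The case against.** The strongest reply is that ANCOVA does not cause the loss of rescued subjects' later values. The period definition does, and an MMRM under 6.3.2 leaves out the same values. MMRM adds only pre-rescue scores, and adds nothing for subjects lost before Week 32. Early rescue is possible, since one trigger in Protocol 7.8.2 needs a single retreatment dose. This stands and limits the gain.

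Second, the protocol itself plans a descriptive summary by treatment, so bringing Table 6.3 into line with that would also end the contradiction. This stands in part. The summary belongs in the report, but on its own it would leave 6.2.2 and 6.3.2 unmet and would treat these instruments differently from PASI, BSA and PSSI.

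Third, with post-rescue data removed, the MMRM mean is a hypothetical one, as if rescue had not happened. It is neither the mean that subjects experienced nor the rescue-as-failure rule used for binary responses. That is correct and should be stated with the result.

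A reader might go further and infer that all rescued and discontinued subjects vanish because of ANCOVA, or that MMRM would return the true group mean. The documents support neither. Subjects who only stop treatment keep attending, rescue concerns PRN subjects alone, and its trigger is PASI, which a model of PRO scores does not contain.

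**Conclusion.** The contradiction is in the text and needs no assumption: four maintenance rows of Table 6.3 break the SAP's own rule, with no reason given. The consequence follows from three SAP provisions taken together: no visit term in the ANCOVA, no imputation of continuous maintenance data, and a period that ends at rescue.

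The size rests wholly on assumed inputs. With 10% to 30% lost after Week 32 and correlation 0.4 to 0.8, the observed-only Week 52 mean is too favourable by about 0.05 to 0.27 SD, or 0.08 to 0.40 SD if exactly the worst scorers are lost. MMRM removes this when loss depends on the earlier PRO score and only part of it when PASI drives the loss.

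The matter is minor. It touches secondary maintenance estimates with no planned comparison between groups, and the Week 16 primary analysis is unaffected.

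**What to change.** - In Table 6.3, change the maintenance method for DLQI, SF-36, PatGA and PSS change from baseline from ANCOVA to MMRM over Weeks 32, 52 and 104, using pre-rescue visits only, as 6.3.2 already provides.
- Align the maintenance sentence in 6.1.3 with that. Keep the protocol's by-treatment mean change and 95% confidence interval, labelled as an observed-case summary.
- State in one sentence that the MMRM mean is the one expected without rescue, and that DLQI records from PRN-dosing or rescue visits outside the three scheduled weeks are not model visits.
- Reconcile the PSS entry in Table 6.2, which names Visit 28 (Week 100, Day 700 ± 5), with the Week 104 window in Appendix 2 (Days 715 to 742).

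The cost is four table cells and a few sentences. The model is already specified for PASI, BSA and PSSI in the same period, and no new data are needed.

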6.3. Handling of Dropouts or Missing Data

6.3.1. Non-Responder Imputation (NRI)

Analysis of categorical efficacy and health outcome variables will be assessed using a NRI method. Subjects will be considered a non-responder for the NRI analysis if they do not meet the clinical response criteria or have missing clinical response data at the analysis time point. Randomized subjects without at least 1 postbaseline observation will also be defined as non-responders for the NRI analysis.

Due to the design, PRN subjects who got rescued will get a different treatment (300 mg LY SC Q8W), therefore the subsequent visits following the first dose of rescue treatment will be defined as non-responders in the analysis for the Maintenance Period.

6.3.2. MMRM

MMRM will be the primary analysis method for longitudinal continuous measurements. It assumes missing data can bias results but the bias can be attenuated by modeling random effects using the within-subject error correlation structure. These correlations between the repeated measurements provide the platform used to account for the bias from subject dropout. MMRM model details are provided in Section 6.1.3.

If subjects enter the Rescue Period, only the visits prior to entering the Rescue Period will be included in the MMRM model for the Maintenance Period efficacy analysis.

6.3.3. mBOCF

An mBOCF analysis will be performed on key continuous efficacy endpoints in the Induction Period only, including PASI, BSA, PSSI, and PSS.

The above is proposed as a sensitivity analysis. For patients discontinuing investigational product due to an AE, the baseline observation will be carried forward to the corresponding primary endpoint for evaluation. For patients discontinuing investigational product for any other reason, the last nonmissing postbaseline observation before discontinuation will be carried forward to the corresponding primary endpoint for evaluation. Randomized patients without at least 1 postbaseline observation will not be included for evaluation with the exception of patients discontinuing study treatment due to an AE.

6.3.4. As Observed

In the Rescue Period, the efficacy endpoints will be summarized as observed. Only descriptive statistics will be reported. No comparisons will be done in this period.

6.4. Multiple Comparisons/Multiplicity

No multiplicity adjustment is planned for this Phase 2 study.

6.5. Subject Disposition

Subject flow will be summarized from entered to randomized to completion, and analysis populations will be listed and summarized by treatment group and visit.

Subject allocation by geographic region, country, and center will be summarized with number of subjects who entered the study, number of intent-to-treat (ITT) subjects for each treatment group, number of subjects discontinued from study treatment, number of subjects discontinued from study, and reasons for discontinuation.

Subject disposition will be summarized for each treatment period by visit. Reasons for discontinuation from the study will be tabulated by treatment randomized.

All subjects who are included in the ITT population and discontinued from the study will be listed, and the extent of their participation in the study will be reported for Induction Period, Maintenance Period, and Posttreatment Follow-up Period. If known, a reason for their discontinuation will be given.

6.6. Subject Characteristics

Subject characteristics and baseline clinical measures will be summarized for each treatment period. Baseline characteristics will include gender, age, age category, body weight, race, geographic region (US/OUS), baseline disease severity, duration of disease, prior exposure to biologic therapy (yes/no), previous nonbiologic systemic therapy, and previous biologic therapy. Baseline clinical measurements will include PASI total score, sPGA score, BSA, PSSI for subjects with scalp psoriasis involvement at baseline or who developed scalp psoriasis postbaseline, PSS total score and item score, PatGA, DLQI total score, SF-36 Physical Component Score (PCS), and SF-36 Mental Component Score (MCS).

No inferential analysis for the comparability of baseline covariates across treatment groups will be performed.

Subject demographic variables and baseline characteristics will be summarized by dose and overall for ITT population with the baseline values defined for the Induction Period. The continuous variables will be summarized using descriptive statistics (N, mean, standard deviation, minimum, Q1, median, Q3, and maximum) and the categorical variables will be summarized using frequency counts and percentages.

For the Maintenance and Follow-up populations, subject demographic variables and baseline characteristics will be summarized using the baseline as defined in Section 6.1.2.

The following demographic variables and baseline characteristics will be summarized:

- Age (in years): calculated using an imputed date of birth of July 1st in the year of birth collected in the electronic case report form (eCRF). Age will be calculated as:
 - $\text{Age} = \text{floor}(\text{intck}(\text{'month'}, \text{brthdtc}, \text{rfstdtc}) - (\text{day}(\text{rfstdtc}) < \text{day}(\text{brthdtc}))) / 12$
 - where brthdtc = Imputed date of birth, and rfstdtc = subject reference start date (that is, the date when subject is first exposed to study treatment)
- Age group: <65 years, ≥65 years
- Age group: <40 years, ≥40 years
- Gender
- Age groups within gender
- Race
- Ethnicity

- Geographic region: United States (US), Other (Non-US): Canada, Germany, Japan, Poland
 - Height (cm): measured at Visit 1
 - Weight (kg): measured at Visit 2
 - Weight category:
 - <80 kg, ≥80 kg
 - <100 kg, ≥100 kg
 - Body mass index (BMI) (kg/m²): BMI will be calculated as:
 - $BMI (kg / m^2) = \frac{Weight (kg)}{(Height (m))^2}$
 - BMI category: underweight (<18.5 kg/m²); normal (≥18.5 and <25 kg/m²); overweight (≥25 and <30 kg/m²); obese (≥30 and <40 kg/m²); extreme obese (≥40 kg/m²)
 - Alcohol use: never, current, former
 - Caffeine use: never, current, former
 - Tobacco use: never, current, former
 - Previous psoriasis therapy:
 - Previous systemic therapy: never used, non-biologic only, biologic only, biologic and non-biologic.
 - Previous non-biologic systemic therapy: never used, ever used
 - Previous biologic therapy: never used, ever used
 - Previous topical therapy: never used, topical prescription therapy, topical non-prescription therapy
 - Previous phototherapy (ultraviolet B [UVB] or PUVA): never used, ever used
- where
- Non-biologics include: methotrexate, cyclosporine, corticosteroids, acitretin, fumaric acid derivatives, apremilast, other
 - Biologics include: efalizumab, ustekinumab, infliximab, etanercept, alefacept, adalimumab, golimumab, certolizumab pegol, secukinumab, ixekizumab, other
- Duration of psoriasis (in years): Will be calculated using the date of psoriasis onset (as recorded on the Prespecified Medical History - Indication eCRF page) as follows:

$$\begin{aligned} & \textit{Duration of psoriasis (years)} \\ = & \frac{\textit{Date of informed consent} - \textit{Date of psoriasis onset}}{365.25} \end{aligned}$$

- Duration of psoriasis diagnosis (in years): Will be calculated using the date of psoriasis diagnosis (as recorded on the Prespecified Medical History - Indication eCRF page) as follows:

$$\begin{aligned} & \textit{Duration of psoriasis diagnosis (years)} \\ = & \frac{\textit{Date of informed consent} - \textit{Date of psoriasis diagnosis}}{365.25} \end{aligned}$$

- Baseline PASI score
- Baseline PASI category: $<20, \geq 20$
- Baseline PASI category: $<15, \geq 15$
- Baseline sPGA
- Baseline sPGA category: 0, 1, 2, 3, 4, 5
- Scalp psoriasis: yes, no (reported on Psoriasis Involvement eCRF form)
- Baseline PSSI score
- Baseline PSS score
- Baseline BSA (%)
- Baseline BSA category: $<20\%, \geq 20\%$
- Baseline DLQI total score
- Baseline DLQI total category: $<10, \geq 10$
- Baseline DLQI total category: $<5, \geq 5$
- Baseline DLQI total category: 0 or 1, >1
- Baseline SF-36 physical functioning score
- Baseline SF-36 role-physical score
- Baseline SF-36 role-emotional score
- Baseline SF-36 bodily pain score
- Baseline SF-36 vitality score
- Baseline SF-36 social functioning score
- Baseline SF-36 mental health score
- Baseline SF-36 general health score
- Baseline SF-36 physical component score

- Baseline SF-36 mental component score.

By-subject listings of demographic and baseline characteristics, respectively, for the ITT population will be provided.

